3.1.3 Definition of Treatment Failure

Treatment failure is the occurrence of any one of the following events:

- After disease control has been achieved, a two-step increase in prednisone (or equivalent) dose to ≥ 20 mg/day for more than 2 weeks to treat increased disease activity during the corticosteroid taper
- Failure to achieve disease control after receiving 240 mg/day PO prednisone (or equivalent) for 1 week

Disease control is defined as the time at which new lesions cease to form and established lesions begin to heal (beginning of the consolidation phase).

- Increase in MMF/matching placebo dosage above 2 g/day
- Initiation of any rescue therapy (addition of another immunosuppressive medication, additional rituximab open-label doses, IV Ig, plasmapheresis, or another treatment or procedure) as determined by the investigator's best medical judgment

Patients experiencing treatment failure prior to achieving sustained complete remission will be categorized as non-responders in the primary analysis, but will continue to be followed in the study per the schedule of assessments. Patients who achieve sustained complete remission without experiencing an event constituting treatment failure beforehand will not be categorized as non-responders, regardless of whether they subsequently meet the criteria during the remaining treatment period.

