3.1.2 Corticosteroid Treatment

Patients eligible for this study will be receiving 60–120 mg/day background oral prednisone or equivalent (1.0–1.5 mg/kg/day) at study entry. During the screening period (up to 28 days), the daily corticosteroid dose may be tapered, as directed by the investigator on the basis of disease activity and tolerability to reach a dosage of 60 or 80 mg/day by Day 1. Thereafter, corticosteroid treatment should then be tapered according to the treatment guideline in [Table 1](#), which provides recommended doses based on the presence of disease activity, defined as the appearance of new lesions or the extension of established lesions. The decision to taper the corticosteroid dose can be affected by physician preferences, patient tolerability, and local practices, among

Rituximab—F. Hoffmann-La Roche Ltd
32/Protocol WA29330, Version 5

other considerations. The oral corticosteroid dose may be increased during the study as needed as the primary intervention for control of disease activity. Prednisone (or equivalent) will be sourced locally.

The goal of study treatment is to maintain disease control and ultimately achieve disease remission. Oral corticosteroids will be tapered to the target prednisone (or equivalent) dosage of 0 mg/day by Week 24 (or sooner, if appropriate). From Week 24 to Week 52, the corticosteroid dosage should be maintained at 0 mg/day. However, patients who experience a disease flare (as defined in Section 3.4.1.2) at 0 mg/day should restart at Step 5 of [Table 1](#) (20 mg/day). Patients whose disease is not controlled after increasing the corticosteroid dose up to an allowable maximum dose of 240 mg/day will be considered to have experienced treatment failure and may receive standard-of-care treatment per the investigator's best medical judgment. Use of minimal concomitant topical corticosteroids will be permitted at the investigator's discretion but will be tracked carefully during the course of the study.

Table 1 Corticosteroid Treatment Guideline

Step	No. of Weeks	Daily Dose of Prednisone or Equivalent	Presence of Disease Activity ^a	
			No	Yes
1 (start) ^b	1 week	80 mg	Go to Step 2	Go to Step A
A	1 week	120 mg	Go to Step 2	Go to Step B
B	1 week	240 mg	Go to Step A	Discontinue taper ^c
2 (start) ^b	1 week	60 mg	Go 1 step forward	Go to Step 1
3	1 week	40 mg		Go 1 step back
4	2 weeks	30 mg		Go 2 steps back
5	2 weeks	20 mg		
6	2 weeks	15 mg		
7	2 weeks	12.5 mg		
8	2 weeks	10 mg		
9	2 weeks	7.5 mg		

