10	2 weeks	5 mg		
11	2 weeks	2.5 mg		
12	During complete remission	0 mg		Restart at Step 5

Notes: On Day 1, start the oral corticosteroid regimen with an initial dosage of 60 or 80 mg/day prednisone (or equivalent), as outlined in the schedule. Increase the dose if disease activity is present after 1 week. If necessary, increase the dose again (to 240 mg/day) if disease activity is still present after the second week.

^a Disease activity is defined as the appearance of new lesions or the extension of established lesions.

^b Patients on 80 mg/d on Day 1 will start at Step 1. Patients on 60 mg/d on Day 1 will start at Step 2.

^c Patients whose disease is not controlled after increasing the corticosteroid dose to 240 mg/day will be considered to have experienced treatment failure and may receive standard-of-care treatment per the investigator's best medical judgment.

Source: Modified from Mentink LF, Mackenzie MW, Tóth GG, et al. Randomized controlled trial of adjuvant oral dexamethasone pulse therapy in pemphigus vulgaris (PEMPULS Trial). *Arch Dermatol* 2006;142:570–6.

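### After one week at 240 mg/day, the steroid table steps a never-controlled patient with static, non-healing lesions down to 120 mg/day, although the failure definition already makes that patient a treatment failure

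*Protocol*

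**What the plan says.** **Failure rule.** Protocol 3.1.3 counts as treatment failure: "Failure to achieve disease control after receiving 240 mg/day PO prednisone (or equivalent) for 1 week". It then states: "Disease control is defined as the time at which new lesions cease to form and established lesions begin to heal". SAP 4.2 carries the same criterion and the same definition.

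**Dosing table.** Protocol 3.1.2 says that Table 1 gives "recommended doses based on the presence of disease activity, defined as the appearance of new lesions or the extension of established lesions". Step B is 240 mg/day for one week. In the *No* activity column the patient goes to Step A (120 mg/day). In the *Yes* column the entry is "Discontinue taper", and that cell alone carries footnote c: "Patients whose disease is not controlled after increasing the corticosteroid dose to 240 mg/day will be considered to have experienced treatment failure". SAP Appendix 4 reproduces the table and its footnotes.

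**Consequences.** Under protocol 3.1.1 and Appendix 1 footnote a, a failure before Week 12 requires an early withdrawal visit and entry to safety follow-up. From Week 12 no withdrawal visit is required. SAP 4.7.1.4 excludes a patient's data from the first point at which any failure criterion is met.

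**The concern.** The table and the failure rule look at the same patient, at the same dose, after the same week, but test different things. Activity does not refer to healing; control does. A site working from the table can therefore step the dose down to 120 mg/day without noticing that the patient has failed.

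Before Week 12 that could mean a missed withdrawal visit and a patient who stays on the taper. At any time, an unrecorded failure means that the cut in SAP 4.7.1.4 is not applied, and a later remission could be counted as response. The other steroid-based criterion in 3.1.3 does not back this up, because it applies only once control has been achieved. The remaining criteria (a study-drug dose above 2 g/day, or rescue) would register only if one of those events occurred later.

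**Working it through.** The plan gives no figure on this point, so the check sets the two rules side by side and then works out the timing.

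**1. Logic table after one week at 240 mg/day, for a patient never yet controlled.** Inputs are the activity definition in Table 1 footnote a and the control definition in 3.1.3. One assumption is made: an extending lesion is not a healing one.

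| New lesions | Established lesions | Table 1, Step B | Protocol 3.1.3 | Agree? |
|---|---|---|---|---|
| Yes | Extending | Active: stop taper | Failure | Yes |
| Yes | Static | Active: stop taper | Failure | Yes |
| Yes | Healing | Active: stop taper | Failure | Yes |
| No | Extending | Active: stop taper | Failure | Yes |
| No | Static | Not active: Step A | Failure | **No** |
| No | Healing | Not active: Step A | Controlled | Yes |

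The table calls 4 states active and 2 inactive; 3.1.3 calls 5 failures and 1 controlled. They differ in one state. This is a count of logical states, not a frequency of patients.

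**2. Only Step B is affected.** Steps 1 and A use the same activity trigger, but 3.1.3 attaches no failure test to 80 or 120 mg/day.

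**3. Timing under uninterrupted escalation from Day 1.**
- Start at 80 mg/day: Steps 1, A, B = 3 × 7 = 21 days, so the decision falls on Day 1 + 21 = Day 22.
- Start at 60 mg/day, following the table rows: Steps 2, 1, A, B = 4 × 7 = 28 days, so Day 29.
- Start at 60 mg/day, following the note under the table ("increase the dose again (to 240 mg/day) if disease activity is still present after the second week"): 3 × 7 = 21 days, so Day 22.

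Week 12 is Day 84. The margins are 84 − 22 = 62 days and 84 − 29 = 55 days, so the withdrawal rule applies on these paths.

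**4. Timing when escalation is interrupted.** By the table, a patient can follow Steps 2, 3, 4, 5, 6 (1 + 1 + 2 + 2 + 2 = 8 weeks), go back two steps to Step 4 (2 weeks), then to Steps 2, 1, A, B (4 × 1 week). The total is 8 + 2 + 4 = 14 weeks, so a first Step B decision can come after Week 12. Had this patient been controlled earlier, the other steroid criterion would probably already apply: the rise from 15 to 30 mg/day lasts 2 weeks and is followed by 60 mg/day, which is more than 2 weeks at 20 mg/day or above.

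**5. Visits.** Appendix 1 schedules Day 15 (±1) and Day 28 (±3). Day 29 falls inside the second window; Day 22 falls in neither.

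**The case against.** **Table 1 only recommends doses, while 3.1.3 defines an outcome.** This stands in part. Section 3.1.2 allows for physician preference, and no text forbids 120 mg/day in a failed patient. However, Step B also carries the failure classification through footnote c, and there it pairs failure with stopping the taper, not with Step A.

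**The right rule is already at hand.** The text of 3.1.2 refers to "Patients whose disease is not controlled after increasing the corticosteroid dose up to an allowable maximum dose of 240 mg/day", and footnote c and protocol 3.3.4 also speak of disease not being controlled. This supports the reading in 3.1.3, and a site that checks that section gets the right answer. But none of the three restates the healing requirement, and the footnote is marked only on the cell that the static patient does not reach.

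**A failure could be reconstructed from the data.** SAP 4.7.2.1 has start and stop dates for each steroid dose, SAP 4.7.2.4 refers to an investigator-determined date of control, and SAP 4.3 summarises failures with reasons. That lowers the risk. SAP 4.2 and 4.7.1.4 do not say that the failure date will be derived from these fields.

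**Readings that go too far.** A reader might infer that a first Step B always precedes Week 12; step 4 of the working shows otherwise. A reader might extend the point to every patient with static lesions; for one controlled earlier, whether control has failed to be achieved is open to interpretation. A reader might also infer that the primary endpoint is ambiguous or that power changes. The endpoint rule is determinate, and the documents give no count from which to estimate an effect on response rates or power.

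**Conclusion.** The mismatch is real and is present in both documents, but it is minor. It concerns one row of one table and one clinical state: a patient never yet controlled whose lesions, after a week at 240 mg/day, are neither new, nor extending, nor healing. It rests on the definitions as written and on treating an extending lesion as not healing.

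The consequence before Week 12 is a possible missed withdrawal visit. At any time it is a possible unrecorded failure, with post-failure data then used for that patient. The documents do not say how many patients reach 240 mg/day or are static a week later; the number is probably small. No endpoint definition, sample size or power figure needs to change.

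**What to change.** In protocol Table 1 and SAP Appendix 4, make the Step B row depend on disease control as defined in 3.1.3. If controlled, go to Step A. If not controlled, discontinue the taper and record treatment failure under footnote c. At a minimum, attach footnote c, with the 3.1.3 definition written into it, to both Step B cells. Leave 3.1.3 and SAP 4.2 unchanged, so that the endpoint does not move, and notify sites.

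The cost is the wording of one row in two documents and a note to sites. SAP 4.7.3.10 refers to disease control as an eCRF value, so no new field appears to be needed. The small downside is that the decision calls for a judgement on healing, which may fall between scheduled visits (Day 22, for example) and could need an unscheduled examination.

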3.1.4 Independent Data Monitoring Committee

Safety data will be reviewed by an independent Data Monitoring Committee (iDMC) as specified in the iDMC Charter and at the following times, whichever occurs first:

- After the first 10 patients have completed at least 3 months of study treatment or have withdrawn early from the study
- After the first 5 telemedicine (TM) patients have completed at least 3 months of study treatment or have withdrawn early

Thereafter, meetings will be held approximately every 4 to 6 months (frequency may be adjusted during the recruitment period), after 10 TM patients have completed at least 3 months of study treatment or withdrawn early from the study, or as requested by the iDMC.

The safety evaluations will be detailed in the iDMC Charter and will include review of conventional safety variables, such as serious adverse events, infusion-related reactions, and infections. Any safety event that requires unblinding will be immediately reported to the iDMC and to the U.S. Food and Drug Administration (FDA) in a U.S. Investigational New Drug (IND) safety report. The iDMC may request and review any additional reports outside of the planned analyses at any time if deemed necessary to ensure the safety of patients. The iDMC will also review the TM data (see Section 7.3). After reviewing safety data, the iDMC will make recommendations regarding continuation, termination,

Rituximab—F. Hoffmann-La Roche Ltd
35/Protocol WA29330, Version 5

or modification of the study. The details of the iDMC roles and responsibilities and the logistics of the iDMC activities will be outlined in an iDMC Charter.

3.2 END OF STUDY

The end of the study is defined as the date when the last patient, last visit (LPLV) occurs. LPLV is expected to occur approximately 2 years after the last patient is enrolled, assuming a 52-week treatment period and a 48-week SFU period for the last patient.

3.3 RATIONALE FOR STUDY DESIGN

3.3.1 Rationale for Rituximab Dose and Schedule

In 2006, rituximab was approved by the FDA for use in RA at a dosing schedule in adults that is irrespective of body weight (i.e., 2×1000 mg IV [Days 1 and 15 with repeated infusions between Months 4 and 6]). Rituximab is under investigation in this study as an experimental drug in PV and is currently not approved for the treatment of patients with PV.

In previous studies of rituximab in PV, investigators have used the proposed 2 × 1000 mg IV dose in the initial cycle (Days 1 and 15) as well as 4×375 mg/m² IV dose (Days 1, 8, 15, and 22). If a 70-kg person of average height were to be treated with the 375 mg/m² approach, the total dose for their initial cycle would be approximately 2.8 g, versus 2 g if the 2×1000 mg IV approach were used. PV (like RA) is an autoimmune disease, and an effective treatment does not require depletion of malignant B-cell clones, as in lymphoma ([Leshem et al. 2013](#)). Given the experience with 2×1000 mg IV dose in autoimmune indications, the literature supporting this dose in PV patients, and the fact that this dose results in a lower total exposure and fewer infusions, the Sponsor has selected this dose and schedule for this trial.

In RA, the rituximab dose 2×1000 mg IV (Days 1 and 15) has been demonstrated to be an effective dose, sufficient to sustain B-cell depletion for 6–9 months. Achieving other therapeutic outcomes in PV, such as complete removal of autoantibodies via sustained B-cell depletion in both the periphery and secondary lymphoid organs, is also a target in the management of PV. Sustained complete remission is the ultimate therapeutic goal. A single cycle of rituximab, although generally effective for at least 6 months (24 weeks), is not considered a cure in this autoimmune-relapsing disease. In RA, it is recommended that, until the desired treatment target is reached, drug therapy should be repeated at least every 6 months ([Smolen et al. 2010](#)). Additionally, a recent clinical trial investigating the use of rituximab in patients with severe and/or refractory pemphigus (84 PV patients; 8 pemphigus foliaceus patients) showed that patients who do not achieve remission after 1 cycle and those who experience relapse benefit from further cycles of rituximab. This recent study suggested that the majority of PV patients receiving a single cycle of rituximab will experience a disease flare, further supporting the rationale for an additional treatment cycle at 6 months ([Heelan et al. 2014](#)).

Rituximab—F. Hoffmann-La Roche Ltd
36/Protocol WA29330, Version 5

3.3.2 Rationale for Active Comparator Arm (MMF)

Corticosteroids are felt to be the mainstay of initial therapy for PV patients, and 64% of patients with mild-to-moderate disease achieved a complete remission with initial corticosteroid infusion and prednisone taper without the use of additional immunosuppressants (Beissert et al. 2010). Patients who have persistent disease that is not fully responsive to corticosteroid treatment and those who have a higher risk of prednisone-related complications require additional immunosuppressive therapy (i.e., typically with azathioprine [2 mg/kg PO] or MMF [2 g/day PO]) (Grundmann-Kollmann et al. 1999; Nousari et al. 1999; Powell et al. 2003; Marzano et al. 2006; Sarma and Ghosh 2007; Zwerner and Fiorentino 2007; Doukaki et al. 2011; Strowd et al. 2011; Eskin-Schwartz et al. 2011, 2012; Ioannides et al. 2012; Almuğairen et al. 2013; Vyas et al. 2013). A comparison of these two therapies concluded that MMF was slightly better at inducing remission and was associated with fewer adverse events (Beissert et al. 2006).

MMF (CellCept®) is marketed in oral and intravenous dosage forms and is currently approved for the prophylaxis of organ rejection in patients receiving allogeneic renal, cardiac, or hepatic transplants. For these approved uses, concomitant treatment with cyclosporine and corticosteroids is recommended.

Clinical studies have investigated the use of MMF in other populations, and MMF is currently used to treat other conditions, including PV; however, it is not approved for indications unrelated to organ transplant. As such, MMF is under investigation in this study as an experimental drug in PV and is currently not approved for the treatment of patients with PV. For additional information on the approved indications and relevant safety information, see the local prescribing information for MMF.

The International Pemphigus and Pemphigoid Society has published treatment recommendations that were generated by consensus, and these support the use of either MMF or azathioprine. Internal marketing data from the Sponsor on U.S. practice has determined that a higher proportion of U.S. dermatologists use MMF versus azathioprine (33% vs. 25%, respectively [internal data]), further confirming that MMF is a significant part of the standard-of-care treatment for PV patients. Multiple publications have assessed the efficacy and safety of MMF in the treatment of PV (Eskin-Schwartz et al. 2011).

MMF has typically been prescribed at 2 to 3 g/day given in divided doses in immunologic (non-transplant) indications. A pivotal, prospective, company-sponsored study was conducted that examined the use of MMF for the treatment of PV patients with mild-to-moderate disease. While this study did not meet its primary endpoint of complete remission (i.e., absence of new, persistent oral or cutaneous lesions, and prednisone dose \leq 10 mg/day from Weeks 48–52), it identified that a dose of 2 g/day is considered to be equally effective to 3 g/day when evaluating secondary endpoints, including time to response and duration of response. MMF is associated with

Rituximab—F. Hoffmann-La Roche Ltd
37/Protocol WA29330, Version 5

dose-limiting toxicity, particularly gastrointestinal and hematologic toxicities, and doses above 3 g/day are not typically used in PV (Beissert et al. 2010). Dose adjustments above 2 g/day are not recommended.

For these reasons, MMF has been selected to be the active comparator in this study. The proposed MMF dosing of 2 g/day PO is consistent with the CellCept® U.S. Package Insert, publications, and guidelines, and represents a strong clinical comparator in the proposed study.

3.3.3 Rationale for Use of the PDAI as the Key Assessment of Disease Activity

Several different instruments assessing clinical disease activity have been developed to capture distribution, activity, and severity of pemphigus. The most commonly used instrument is the PDAI, developed by the International Pemphigus Committee (Murrell et al. 2008; Rosenbach et al. 2009; Daniel et al. 2012). Rahbar et al. (2014) evaluated the PDAI and a number of other validated instruments in a large number of patients with PV. Inter-rater reliability and convergent validity according to anti-Dsg titers (which correlate with pemphigus disease activity) were evaluated, and the authors concluded that the PDAI had the highest reliability and validity. It is recommended for use in multicenter studies of rare diseases, such as PV. The PDAI can be completed in less than 5 minutes. The PDAI will provide a reliable and validated measurement of disease activity and severity in this study.

3.3.4 Rationale for Corticosteroid Treatment Guidelines

There is no uniformly accepted taper regimen for oral corticosteroids. The initial use of high-dose systemic corticosteroids, typically 60–120 mg/day PO prednisone or equivalent (1.0–1.5 mg/kg/day) is frequently used in the treatment of moderate-to-severely active disease. Recent studies employed a similar regimen and suggest that a dose of 1.0–1.5 mg/kg per day PO prednisone (or equivalent) tapered over 3–6 months is a standard regimen (Beissert et al. 2006, 2010). The decision to taper can be affected by various considerations, including physician preferences, patient tolerability, and local practices.

The rate at which corticosteroids are tapered in this study is based on the clinical manifestations of the disease, and tapering too rapidly increases the chances of a disease flare. The suggested taper and initial dose were discussed with expert advisors in an advisory board and deemed desirable (Advisory Board Meeting 12 February 2014). Patients who experience disease flare will receive an increase in prednisone up to 240 mg/day at the investigator's discretion. Patients who require prednisone 240 mg/day for 1 week and are still not controlled and patients who require a two-step increase in prednisone dose to ≥ 20 mg/day for more than 2 weeks to treat increased disease activity during the corticosteroid taper will be considered non-responders in the primary efficacy analysis. There are additional treatment failure criteria that lead to protocol-defined non-response, outlined in Section 3.1.3.

Rituximab—F. Hoffmann-La Roche Ltd
38/Protocol WA29330, Version 5

3.3.5 Rationale for Biomarker Assessments, including Optional Whole Blood and Serum Samples for Storage and Future Research

PV is a heterogeneous disease, and anti-Dsg1 and anti-Dsg3 autoantibodies expression has been shown to vary among patients (Harman et al. 2001). Autoantibody titers may influence responses to rituximab or MMF. Predictive biomarker samples collected during the study will be assessed in an effort to identify those patients with autoantibody-driven pathogenesis and, potentially, those who are most likely to respond to rituximab.

Identification of proteins targeted by autoantibodies in PV is a subject of intense research. There is evidence that keratinocyte antigens other than Dsg1 and Dsg3 are pathophysiologically relevant (Nguyen et al. 1998). Current understanding, however, does not adequately explain the mechanism of acantholysis in patients lacking anti-Dsg1 and anti-Dsg3 antibodies. Results of a recent study indicate that autoreactivity in PV relies on somatic mutations generated in response to an antigen unrelated to Dsg3 (Di Zenzo et al. 2012). Taken together, these observations justify a search for novel targets of pemphigus autoimmunity via collection of additional optional blood samples for the Roche Clinical Repository (RCR) for storage and future research in PV. These samples include serum for biomarker analysis and whole blood samples for RNA and DNA analysis.

Other pharmacodynamic (PD) biomarkers, including CD19, will be assessed to demonstrate evidence of biologic activity of rituximab in patients and to inform potential revisions to the PK sample collection schedule. As these biomarkers may also have prognostic value, their potential association with disease progression will also be explored.

